## **9. RESEARCH METHODS**

### **9.1 STUDY DESIGN**

The proposed study will utilize data from the Truven MarketScan dataset (US).

The Truven MarketScan databases are comprised of two components: the MarketScan Commercial Claims and Encounters (CCAE) Database and the Medicare Supplemental and Coordination of Benefits (COB) Database. These databases capture longitudinal, individual-level data on healthcare utilization, healthcare expenditures and plan enrollment, and contain integrated records for patient demographics, inpatient events, outpatient events, and pharmacy dispensing of drugs. The CCAE database is a medical and drug insurance claims database on ~150 million patients since from 2008 unique de-identified patients that include active employees, dependents, retirees or recipients of the Consolidated Omnibus Budget Reconciliation Act (COBRA), and data are drawn from large employers, health plans, and public organizations in the United States (Truven Health MarketScan® Research Databases 2015). The MarketScan Medicare Supplemental and Coordination of Benefits (COB) Database contains pooled medical and drug insurance claims data of approximately 13.6 Million unique de-identified patients (since 1996) that are Medicare-eligible retirees with employer-sponsored Medicare Supplemental plans. (**Truven Health MarketScan® Research Databases 2015**).

In principle, in US when a patient goes to a pharmacy and gets a drug dispensed, the pharmacy bills the insurance carrier for the cost of that drug (**Strom 2013**). For billing purposes, the pharmacy has to identify which medication was dispensed along with the dosage strength (e.g. the milligrams per tablet) and quantity (e.g., number of tablets, etc.). Analogously, when a patient goes to a hospital or to a physician for medical care, the providers of care bill the insurance carrier for the cost of the medical care, and have to justify the bill with a diagnosis. Using a common patient identification number for both the pharmacy and the medical care claims, these elements can be linked, and analyzed as a longitudinal medical record (**Strom 2013**).

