### Matched Cohort

A matched propensity score analysis will be used to assess comparative persistence between the two exposure comparison groups. Logistic regression will be used to calculate the propensity to initiate Olodaterol/Tiotropium Bromide versus Umeclidinium/Vilanterol given all covariates (except components of the Charlson Comorbidity index) listed in [section 9.3.3](#), according to the following model:

$$\text{Logit}(\text{Treatment} | X_1, X_2, \dots, X_n) = \beta_0 + \beta_1 * X_1 + \beta_2 * X_2 + \dots + \beta_n * X_n$$

Any covariates which are collinear with each other will be dropped from the analysis (if it causes failure of model to converge). The propensity score will then be used to identify up to 2 initiators of Umeclidinium/Vilanterol for each initiator of Olodaterol/Tiotropium Bromide with the same propensity score ( $\pm$  a caliper of 5%) as the corresponding initiator of Olodaterol/Tiotropium Bromide (Austin 2011).

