## 9.3 VARIABLES

### 9.3.1 Exposures

- Exposure: Olodaterol/Tiotropium Bromide (Stiolto®) delivered with Respimat inhalator
- Active Comparator: Umeclidinium/Vilanterol (Anoro®) delivered with the Ellipta Inhaler

Both exposures will be identified via NDC Generic Name and NDC Brand Name.

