**Lifestyle**

- Smoking-related claim
- Vaccination for Influenza
- Vaccination for Pneumococcus

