**9.4 DATA SOURCES**

The proposed study will utilize data from Truven MarketScan data (US).

The Truven MarketScan databases capture longitudinal, individual-level administrative claims data from the United States. The data available for the study includes three components of MarketScan: the Commercial Claims and Encounters (CCAE) Database, the Medicare Supplemental and Coordination of Benefits Database (MDCR), and the Medicaid Database. Patients in the databases include active employees, dependents, retirees, COBRA recipients, and Medicare or Medicaid enrollees. Data were drawn from large employers, health plans, and public organizations in the United States. The following tables of the MarketScan databases were available for analysis: Enrollment Detail, Inpatient Admissions, Inpatient Services, Outpatient Services, Outpatient Pharmaceutical Claims, and Long Term Care. These tables provide information on plan enrollment, healthcare utilization and expenditures, demographics, and integrated records for inpatient events, outpatient events, and pharmacy dispensings. Data are available from January 1, 2008 to March 31, 2018, and represent approximately 162 million patients.

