Peptic Ulcer Disease	
1 Inpatient or 2 Outpatient (30 – 365 days apart)
 
Diagnosis Code (Any Position), ICD-9 is any of: { “531”, “531.0”, “531.00”, “531.01”, “531.1”, “531.10”, “531.11”, “531.2”, “531.20”, “531.21”, “531.3”, “531.30”, “531.31”, “531.4”, “531.40”, “531.41”, “531.5”, “531.50”, “531.51”, “531.6”, “531.60”, “531.61”, “531.7”, “531.70”, “531.71”, “531.9”, “531.90”, “531.91”, “532”, “532.0”, “532.00”, “532.01”, “532.1”, “532.10”, “532.11”, “532.2”, “532.20”, “532.21”, “532.3”, “532.30”, “532.31”, “532.4”, “532.40”, “532.41”, “532.5”, “532.50”, “532.51”, “532.6”, “532.60”, “532.61”, “532.7”, “532.70”, “532.71”, “532.9”, “532.90”, “532.91”, “533”, “533.0”, “533.00”, “533.01”, “533.1”, “533.10”, “533.11”, “533.2”, “533.20”, “533.21”, “533.3”, “533.30”, “533.31”, “533.4”, “533.40”, “533.41”, “533.5”, “533.50”, “533.51”, “533.6”, “533.60”, “533.61”, “533.7”, “533.70”, “533.71”, “533.9”, “533.90”, “533.91”, “534”, “534.0”, “534.00”, “534.01”, “534.1”, “534.10”, “534.11”, “534.2”, “534.20”, “534.21”, “534.3”, “534.30”, “534.31”, “534.4”, “534.40”, “534.41”, “534.5”, “534.50”, “534.51”, “534.6”, “534.60”, “534.61”, “534.7”, “534.70”, “534.71”, “534.9”, “534.90”, “534.91” }
 
Diagnosis Code (Any Position), ICD-10 is any of: { “K25.0”, “K25.1”, “K25.2”, “K25.3”, “K25.4”, “K25.5”, “K25.6”, “K25.7”, “K25.9”, “K26.0”, “K26.1”, “K26.2”, “K26.3”, “K26.4”, “K26.5”, “K26.6”, “K26.7”, “K26.9”, “K27.0”, “K27.1”, “K27.2”, “K27.3”, “K27.4”, “K27.5”, “K27.6”, “K27.7”, “K27.9”, “K28.0”, “K28.1”, “K28.2”, “K28.3”, “K28.4”, “K28.5”, “K28.6”, “K28.7”, “K28.9” }

Gastroesophageal Reflux Disease	
Any of the following criteria:
 
≥2 medical claims with a primary or secondary ICD-9-CM code for reflux esophagitis (530.11), esophageal reflux (530.81) or heartburn (787.1) or primary or secondary ICD-10-CM code for GERD (K21, K21.0, K21.9) or Heartburn (R12); ≥1 medical claim with a primary or secondary ICD-9-CM 530.11, 530.81 or 787.1 and either (a) ≥1 pharmacy claim for a PPI (esomeprazole, lansoprazole, omeprazole, pantoprazole, rabeprazole), an H2RA (cimetidine, famotidine, nizatidine, or ranitidine) or “other” GERD agent (bethanechol, metoclopramide, sucralfate) or (b) ≥1 medical claim with a primary or secondary ICD-9-CM code for esophageal stricture (530.3) Barrett’s esophagus (530.85), esophageal ulcer (530.2x) or esophagitis (530.1x).

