	
“342.11”, “342.12”, “342.8”, “342.80”, “342.81”, “342.82”, “342.9”, “342.90”, “342.91”, “342.92”, “344.1” }
 
Diagnosis Code (Any Position), ICD-10 is any of: { “G81.00”, “G81.01”, “G81.02”, “G81.03”, “G81.04”, “G81.10”, “G81.11”, “G81.12”, “G81.13”, “G81.14”, “G81.90”, “G81.91”, “G81.92”, “G81.93”, “G81.94”, “G82.20”, “G81”, “G81.9”, “I69.05”, “I69.051”, “I69.052”, “I69.053”, “I69.054”, “I69.059”, “I69.15”, “I69.151”, “I69.152”, “I69.153”, “I69.154”, “I69.159”, “I69.25”, “I69.251”, “I69.252”, “I69.253”, “I69.254”, “I69.259”, “I69.35”, “I69.351”, “I69.352”, “I69.353”, “I69.354”, “I69.359”, “I69.85”, “I69.851”, “I69.852”, “I69.853”, “I69.854”, “I69.859”, “I69.95”, “I69.951”, “I69.952”, “I69.953”, “I69.954”, “I69.959”, “G81.0”, “G81.1”, “G82.2”, “G82”, “G82.21”, “G82.22”, “G04.1”, “G11.4” }

	Lifestyle
Smoking-related claim	
1 Inpatient or 1 Outpatient
 
Diagnosis Code (Any Position), ICD-9 is any of: { “305.1”, “V15.82”, “989.84”, “649.0x” }
 
Diagnosis Code (Any Position), ICD-10 is any of: { “F17.2”, “T65.2”, “Z71.6”, “O99.33”, “O99.330”, “O99.331”, “O99.332”, “O99.333”, “O99.334”, “O99.335”, “Z72.0”, “Z81.2” }
 
Procedure Code (Any Position), CPT and HCPC is any of: { “99406”, “99407”, “G0436”, “G0437”, “G9016”, “S9453”, “S4995”, “G9276”, “G9458”, “1034F”, “4004F”, “4001F” }

Vaccination for Influenza/Pneumococcus	
1 Inpatient Service or 1 Outpatient
 
Procedure Code (Position 1), CPT and HCPC is any of: { “4040F”, “90630”, “90653”, “90654”, “90655”, “90656”, “90657”, “90658”, “90659”, “90660”, “90661”, “90662”, “90663”, “90664”, “90665”, “90666”, “90667”, “90668”, “90669”, “90670”, “90672”, “90673”, “90685”, “90686”, “90687”, “90688”, “90732”, “G0008”, “G0009”, “G0919”, “G8108”, “G8115”, “G8864”, “G9279”, “Q0034”, “Q2033”, “Q2034”, “Q2035”, “Q2036”, “Q2037”, “Q2038”, “Q2039”, “S0195” }

Respiratory Function Procedures/Tests	
Pulmonary function tests	1 Inpatient or 1 Outpatient  Procedure Code (Any Position), CPT and HCPC is any of: { “3038F”, “94010”, “94014”, “94015”, “94060”, “94621”, “94720”, “94725”, “94726”, “94727”, “94728”, “94729”, “94750”, “94770”, “94799” }  Procedure Code (Any Position), ICD-9 is any of: { “89.37” }  Procedure Code (Any Position), ICD-10 is any of: { “4A0971Z”, “4A0981Z”, “4A09X1Z”, “4A1971Z”, “4A19X1Z” }

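### The vaccination covariate ignores the pharmacy claims the study holds, so any vaccine billed only as a drug claim would be coded as not given; the likely effect on the treatment comparison is small

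*Combined protocol and SAP*

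**What the plan says.** The Lifestyle part of Annex 4 has one entry for influenza and pneumococcal vaccination. It requires "1 Inpatient Service or 1 Outpatient" event, identified by "Procedure Code (Position 1), CPT and HCPC", followed by a list of procedure codes. No NDC, generic name, brand name or pharmacy claim is mentioned, and the medication list in Annex 3 contains no vaccine.

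Section 9.4 names the tables available for analysis: "Enrollment Detail, Inpatient Admissions, Inpatient Services, Outpatient Services, Outpatient Pharmaceutical Claims, and Long Term Care". Pharmacy claims are thus held, in a table separate from outpatient services. Section 9.3.1 shows how the study finds dispensed products: "Both exposures will be identified via NDC Generic Name and NDC Brand Name".

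Two other Annex 4 measures already use drug data. One route into the gastroesophageal reflux definition pairs a single diagnosis claim with "≥1 pharmacy claim for a PPI (esomeprazole, lansoprazole, omeprazole, pantoprazole, rabeprazole" or another listed agent. The dementia definition lists generic drug names beside its diagnosis codes.

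Section 9.3.3 lists "Vaccination for Influenza" and the pneumococcal equivalent as covariates. The propensity model in section 9.2.2 is fitted "given all covariates (except components of the Charlson Comorbidity index) listed in" section 9.3.3, and the multivariable models in section 9.7.1.3 use the same set.

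**The concern.** A vaccine recorded only in the pharmacy table cannot meet the Annex 4 rule. The patient is then coded as unvaccinated in Table 2, in the propensity score and in the multivariable models, although the record is in the data. This is a gap in the definition, not a limit of the database. The limitations in section 9.9 mention over-the-counter items and physician samples as unobserved, but not this.

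The outcome is continued refilling of an inhaler. Vaccination is a marker of preventive behaviour, and section 9.12 treats the listed covariates as hypothesised confounders. If the groups differ in true vaccination, matching on an incomplete flag leaves part of that difference in place. The matched Cox model has treatment as its only term, so nothing later in the primary analysis would remove it.

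**Working it through.** The plan gives no vaccination prevalence, capture rate or billing share, so there is no figure of its own to reproduce. Only the group sizes come from the documents (section 9.5): 3,889 + 10,862 = 14,751, which agrees with the stated total. Every other input below is an assumption.

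**Patients miscoded.** Assume 30% to 45% are vaccinated in the baseline period and 15% to 35% of those are billed only as drug claims. Among the 3,889 Stiolto initiators:
- low end: 3,889 × 0.30 × 0.15 = 175
- high end: 3,889 × 0.45 × 0.35 = about 613

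**Imbalance left after matching on the flag.** Assume true vaccination of 40% (Stiolto) and 36% (Anoro), no false positives, and sensitivity s of 0.85 or 0.65 (the complement of 15% and 35%). Write p1 = 0.40 and p0 = 0.36. After matching, the comparators have the Stiolto distribution of the flag:
- flagged share = p1 × s
- truly vaccinated among unflagged comparators: q = p0(1 − s) / (1 − p0 × s)
- true vaccination in matched comparators = p1 × s + (1 − p1 × s) × q

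| Step | s = 0.85 | s = 0.65 |
|---|---|---|
| Flagged share | 0.34 | 0.26 |
| q | 0.054/0.694 = 0.0778 | 0.126/0.766 = 0.1645 |
| True vaccination, matched comparators | 0.34 + 0.66 × 0.0778 = 0.3914 | 0.26 + 0.74 × 0.1645 = 0.3817 |
| Difference left | 0.0086 | 0.0183 |
| Share of the 0.04 difference | 22% | 46% |

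In absolute terms, 0.9 to 1.8 percentage points remain. Dividing by √(0.40 × 0.60) = 0.49 gives a standardised difference of about 0.02 to 0.04.

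**Effect on the treatment ratio.** Assume no true treatment effect and a vaccination risk ratio for discontinuation of 0.8. Relative risk in a group is 1 − 0.2 × (true vaccination):
- Stiolto: 1 − 0.2 × 0.40 = 0.92
- comparators, s = 0.85: 1 − 0.2 × 0.3914 = 0.9217; ratio 0.92/0.9217 = 0.998, a shift of about 0.2%
- comparators, s = 0.65: 1 − 0.2 × 0.3817 = 0.9237; ratio 0.92/0.9237 = 0.996, a shift of about 0.4%
- no adjustment for vaccination: 0.92/(1 − 0.2 × 0.36) = 0.92/0.928 = 0.991, a shift of about 0.9%

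With a vaccination risk ratio of 0.7 the shifts are about 0.3% (0.88/0.8826) and 0.6% (0.88/0.8855).

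**Wider range.** The same formulas were run for true vaccination of 40% v 45%, 40% v 50% and 50% v 40%, vaccination risk ratios of 0.7 to 0.9 and sensitivities of 0.5 to 0.9. The shift then runs from about 0.1% to 2.3%, and its sign follows the direction of the assumed imbalance.

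**The case against.** A reader might infer that vaccination is in fact under-adjusted and that the primary hazard ratio is biased. The documents do not support that.

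- **Billing route.** Section 9.1 says that, in principle, "when a patient goes to a pharmacy and gets a drug dispensed, the pharmacy bills the insurance carrier for the cost of that drug". It illustrates this with tablets and does not say how a vaccine given at a pharmacy is billed. One billed as a procedure on a medical claim can be caught by the existing rule. The share billed only as a drug claim is unknown.
- **Imbalance.** Both groups are new users of the same drug class in the same databases. If true vaccination and its capture are alike in both, the gap lowers a count in Table 2 and does not confound the hazard ratio. That the missed patients are more likely to persist is conjecture.
- **Other covariates.** Statins, antihypertensives, antidiabetic agents and other dispensed drugs in section 9.3.3 also reflect pharmacy use, and smoking-related claims and lung function tests reflect engagement with care. Correlated covariates would absorb part of any gap, which the one-variable calculation ignores.
- **General safeguards.** Section 9.12 provides for medical review of code lists, section 9.8 permits changes to measure definitions, and section 9.9 concedes residual confounding.

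All four stand as limits on size and certainty. None removes the gap: the rule as written does not search a table the study holds, and no safeguard names it.

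**Conclusion.** The point holds as a conditional one. Any influenza or pneumococcal vaccine billed only as a drug claim would be missed, which would understate vaccination in Table 2. Only if true vaccination also differs between the groups would it leave slightly incomplete adjustment in the propensity score and the multivariable models.

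The 0.2% to 0.4% shift rests on the assumed 40% v 36%, sensitivity of 0.65 to 0.85 and vaccination risk ratio of 0.8. Actual size and direction cannot be derived from the documents. This is a worthwhile refinement of one covariate among many and does not by itself threaten the primary result.

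**What to change.** In Annex 4, let one outpatient pharmaceutical claim qualify alongside one inpatient service or one outpatient event, and identify influenza and pneumococcal vaccines there by NDC generic and brand name, as section 9.3.1 does for the exposures. Tag each product by vaccine, because section 9.3.3 and Table 2 list the two separately while Annex 4 combines them. The restriction to procedure codes in position 1 is a separate limit that this change does not lift; it can be checked in the same review.

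The cost is building and reviewing a vaccine drug list and one more search of a table already in use. Section 9.8 requires the change to be documented by amendment. No endpoint, hypothesis or model form changes. If the definition is left as it is, section 9.9 should state the gap.

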## **ANNEX 5. TABLE SHELLS AND PROPOSED FIGURES**

**Table 1.** Cohort Selection

	Excluded	Remaining
Eligible Population		
Did not meet cohort entry criteria (use of Tio/Olo or Ume/Vi)		
< 180 days of continuous enrollment		
Prior use of Ume/Vi during 180d washout		
Prior use of Tio/Olo during 180d washout		
Tio/Olo and Ume/Vi both occurring on cohort entry date		
Age <40 years		
No prior diagnosis of COPD any time prior using all available data		
Diagnosis of Asthma any time prior using all available data		
Diagnosis of Lung Cancer any time prior using all available data		
Lung Transplant any time prior using all available data		
Final cohort		

**Table 2.** Patient Characteristics of the Study Population (Unmatched/ Matched)

	Tio/Olo	Umech/Vi	Standardized Difference (95% CI)
N			
Median Follow-up Time [IQR]			
Demographics			
Age on index date			
Mean (SD)			
Median [IQR]			
Gender			
Male; n (%)			
Female; n (%)			
Region			
Northeast; n (%)			
North Central; n (%)			
South; n (%)			
West; n (%)			
Missing/Unknown; n (%)			
Insurance Type			
Commercial; n (%)			
Medicare; n (%)			
Missing; n (%)			
Year of Cohort Entry, n (%)			
First Year (November 17, 2015 – November 30, 2016); n (%)			
Second Year (December 1, 2016 – November 30, 2017); n (%)			
Third Year (December 1, 2017 to March 31, 2018)			
Concomitant Medications			

Proprietary confidential information © 2019 Boehringer Ingelheim International GmbH or one or more of its affiliated companies

	Tio/Olo	Umec/Vi	Standardized Difference (95% CI)
Oral Corticosteroids; n (%)			
Short acting muscarinic antagonist (SAMA), n (%)			
Short acting beta agonist (SABA), n (%)			
Long acting muscarinic antagonist (LAMA), n (%)			
Long acting beta agonist (LABA), n (%)			
Inhaled corticosteroid (ICS), n (%)			
LAMA / LABA combination (not Tio/Olo or Umec/Vi), n (%)			
LABA / ICS combination, n (%)			
LAMA / LABA / ICS combination, n (%)			
NSAIDs, n (%)			
Antihistamines, n (%)			
Opioids, n (%)			
Oral antibiotics, n (%)			
Antidiabetic Agents (not including insulin), n (%)			
Insulin (basal or mealtime), n (%)			
Methotrexate, n (%)			
Statins; n (%)			
Antihypertensives; n (%)			
Anticoagulants; n (%)			
Anti-psychotic/anti-depressives/anxiolytic, n (%)			
Oxygen therapy, n (%)			
Comorbidities/Symptoms			
History of All-Cause Hospitalization; n (%)			
History of Emergency Department Visit; n (%)			
History of Hospitalization due to Respiratory Condition; n (%)			
Acute Myocardial Infarction; n (%)			
Angina Pectoris; n (%)			
Peripheral Vascular Disease; n (%)			

	Tio/Olo	Umech/Vi	Standardized Difference (95% CI)
Heart Failure; n (%)			
Hypertension; n (%)			
Upper Respiratory Tract Infection; n (%)			
Lower Respiratory Tract Infection; n (%)			
Cardiac Arrhythmias; n (%)			
Cerebrovascular Disease; n (%)			
All Cancers (except non-melanoma skin cancer); n (%)			
Allergic Rhinitis; n (%)			
Chronic Sinusitis; n (%)			
Bronchiectasis; n (%)			
Pneumonia; n (%)			
Chronic Bronchitis; n (%)			
Exertional Breathlessness; n (%)			
Anxiety; n (%)			
Dementia; n (%)			
Depression; n (%)			
Osteoporosis; n (%)			
Charlson-Deyo Comorbidity Index, continuous			
mean (sd)			
median [IQR]			
Charlson-Deyo Comorbidity Index, categorical			
0; n (%)			
1; n (%)			
2; n (%)			
3+; n (%)			
Acute Liver Injury or Failure; n (%)			
Chronic Kidney Disease (without ESRD); n (%)			
End Stage Renal Disease; n (%)			
Rheumatologic Disease; n (%)			

	Tio/Olo	Umecl/Vi	Standardized Difference (95% CI)
Peptic Ulcer Disease; n (%)			
Gastroesophageal reflux disease (GERD); n (%)			
Type 1 Diabetes Mellitus; n (%)			
Type 2 Diabetes Mellitus; n (%)			
Type 1 or Type 2 Diabetes with no chronic complications; n (%)			
Type 1 or Type 2 Diabetes with chronic complications; n (%)			
Mild Liver Disease; n (%)			
Moderate to Severe Liver Disease; n (%)			
Renal Disease; n (%)			
Metastatic Solid Tumor; n (%)			
HIV/AIDS; n (%)			
Hemiplegia or Paraplegia; n (%)			
Lifestyle			
Smoking Related Claim or Intervention; n (%)			
Vaccination for Influenza; n (%)			
Vaccination for Pneumococcus; n (%)			
Respiratory Function Procedures/Tests			
Pulmonary function tests; n (%)			
Six-minute walk test; n (%)			
Chest X-ray; n (%)			
Chest HRCT; n (%)			

*Tio/Olo, tiotropium/olodaterol; Umecl/Vi, umeclidinium, vilanterol.*

**Table 3.** Absolute Standardized Differences as Measured in the Unmatched vs. Matched Cohorts

	Abs. Std. Diff. (Unmatched)	Abs. Std. Diff. (Matched)	Change	Change (%)
Demographics				
Age on index date				
Gender				
Region				
Insurance Type				
Year of Cohort Entry				
Oral Corticosteroids; n (%)				
Short acting muscarinic antagonist (SAMA), n (%)				
Short acting beta agonist (SABA), n (%)				
Long acting muscarinic antagonist (LAMA), n (%)				
Long acting beta agonist (LABA), n (%)				
Inhaled corticosteroid (ICS), n (%)				
LAMA / LABA combination (not Tio/Olo or Umecl/Vi), n (%)				
LABA / ICS combination, n (%)				
LAMA / LABA / ICS combination, n (%)				
NSAIDs, n (%)				
Antihistamines, n (%)				
Opioids, n (%)				
Oral antibiotics, n (%)				
Antidiabetic Agents (not including insulin), n (%)				
Insulin (basal or mealtime), n (%)				
Methotrexate, n (%)				
Statins; n (%)				
Antihypertensives; n (%)				
Anticoagulants; n (%)				

	Abs. Std. Diff. (Unmatched)	Abs. Std. Diff. (Matched)	Change	Change (%)
Anti-psychotic/anti-depressives/anxiolytic; n (%)				
Oxygen therapy; n (%)				
Comorbidities/Symptoms				
History of All-Cause Hospitalization; n (%)				
History of Emergency Department Visit; n (%)				
History of Hospitalization due to Respiratory Condition; n (%)				
Acute Myocardial Infarction; n (%)				
Angina Pectoris; n (%)				
Peripheral Vascular Disease; n (%)				
Heart Failure; n (%)				
Hypertension; n (%)				
Upper Respiratory Tract Infection; n (%)				
Lower Respiratory Tract Infection; n (%)				
Cardiac Arrhythmias; n (%)				
Cerebrovascular Disease; n (%)				
All Cancers (except non-melanoma skin cancer); n (%)				
Allergic Rhinitis; n (%)				
Chronic Sinusitis; n (%)				
Bronchiectasis; n (%)				
Pneumonia; n (%)				
Chronic Bronchitis; n (%)				
Exertional Breathlessness; n (%)				
Anxiety; n (%)				
Dementia; n (%)				
Depression; n (%)				
Osteoporosis; n (%)				

Proprietary confidential information © 2019 Boehringer Ingelheim International GmbH or one or more of its affiliated companies

	Abs. Std. Diff. (Unmatched)	Abs. Std. Diff. (Matched)	Change	Change (%)
Charlson-Deyo Comorbidity Index, continuous				
Charlson-Deyo Comorbidity Index, categorical				
Acute Liver Injury or Failure; n (%)				
Chronic Kidney Disease (without ESRD); n (%)				
End Stage Renal Disease; n (%)				
Rheumatologic Disease; n (%)				
Peptic Ulcer Disease; n (%)				
Gastroesophageal reflux disease (GERD); n (%)				
Type 1 Diabetes Mellitus; n (%)				
Type 2 Diabetes Mellitus; n (%)				
Type 1 or Type 2 Diabetes with no chronic complications; n (%)				
Type 1 or Type 2 Diabetes with chronic complications; n (%)				
Mild Liver Disease; n (%)				
Moderate to Severe Liver Disease; n (%)				
Renal Disease; n (%)				
Metastatic Solid Tumor; n (%)				
HIV/AIDS; n (%)				
Hemiplegia or Paraplegia; n (%)				
Vaccination for Influenza / Pneumococcus; n (%)				
Respiratory Function Procedures/Tests				
Pulmonary function tests; n (%)				
Six-minute walk test; n (%)				
Chest X-ray; n (%)				
Chest HRCT; n (%)				

*Tio/Olo, tiotropium/olodaterol; Umec/Vi, umeclidinium, vilanterol.*

**Table 4.** Unmatched Cohort Discontinuation Rates and Risks for Tio/Olo vs. Ume/Vi.

Parameter	Tio/Olo	Ume/Vi
Number of patients		
Number of person-years		
Number of events (discontinuations)		
Rate		
Rate per 1,000 person-years		
Rate Difference per 1,000 person-years (95% CI)		1.0 (Reference)
Rate Ratio (95% CI)		1.0 (Reference)
Risk		
Risk per 1,000 patients		
Risk Difference per 1,000 person-years (95% CI)		1.0 (Reference)
Risk Ratio (95% CI)		1.0 (Reference)
Primary Estimates		
Unadjusted Hazard Ratio (95% CI)		1.0 (Reference)
Fully adjusted Hazard Ratio (95% CI)		1.0 (Reference)

*Tio/Olo, tiotropium/olodaterol; Ume/Vi, umeclidinium, vilanterol.*

**Table 5.** 1:2 Matched Cohort Discontinuation Risk for Tio/Olo vs. Umecl/Vi.

Parameter	Tio/Olo	Umecl/Vi
Number of patients		
Number of person-years		
Number of events (discontinuations)		
Rate		
Rate per 1,000 person-years		
Rate Difference per 1,000 person-years (95% CI)		1.0 (Reference)
Rate Ratio (95% CI)		1.0 (Reference)
Risk		
Risk per 1,000 patients		
Risk Difference per 1,000 person-years (95% CI)		1.0 (Reference)
Risk Ratio (95% CI)		1.0 (Reference)
Primary Estimates		
Matched Hazard Ratio (95% CI)		1.0 (Reference)

*Tio/Olo, tiotropium/olodaterol; Umecl/Vi, umeclidinium, vilanterol.*

